**Visit 1, Study Day 1 (Vaccination Day) - Screening, Enrollment, and Randomization (Clinic Visit)**

- If Screening Visit occurred prior to Visit 1, review and confirm eligibility and all data collected during Screening Visit
- Obtain vital signs including oral temperature prior to vaccination
- Obtain 15mL blood sample prior to vaccination for serologic analysis (Section 6)
- Randomize study participant to simultaneous or sequential vaccine administration (Section 5.2.1)
- Administer assigned study products – Trained, licensed research staff will administer either IIV alone or IIV + Tdap as described in Section 5.2.3. Ensure participants receive corresponding Vaccine Information Sheets (VIS) during visit.
- Dispense memory aid (Appendix B and C), thermometer, and ruler (in order to standardize measurements). Review instructions for use of thermometer, ruler, and

memory aid (Appendix A) completion.

- Confirm preferred method of contact for follow-up (telephone, text or email reminder)
- Confirm date of next scheduled prenatal appointment
- Record any AEs and SAEs during post-vaccination monitoring

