**Visit 4, Study Day 22 (window Days 22 – 29) Clinic Visit**

- For study participants in the sequential study group, review exclusion criteria listed in section 4.2 for Tdap vaccination
- Obtain vital signs including oral temperature prior to vaccination for study participants in the sequential group.
- Study staff will review the memory aid data and record any AEs, SAEs, concomitant medications, and current medical/pregnancy status as described in Section 5.1
- Obtain 15mL blood sample for serologic analysis (Section 6). Study participants in sequential group to have blood sample obtained prior to vaccination.
- For subjects in the sequential study group, trained, licensed research staff will administer Tdap as described in Section 5.2.3. Ensure participants receive Tdap Vaccine Information Sheets (VIS) during visit.
- Confirm subjects still have previously dispensed thermometer and ruler; if not, provide new supplies. Review instructions for use of thermometer, ruler, and memory aid (Appendix A) completion. All subjects will complete the memory aid (Appendix D and E) again to allow for the collection of “mock” data in the simultaneous group for comparison with the sequential group. Simultaneous group will only provide information for systemic reactions and oral temperature.

- Confirm preferred method of contact for follow-up (telephone or email reminder)
- Confirm date of next scheduled prenatal appointment

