### **5.2.1 Randomization**

Participants will be randomized (1:1) to receive either IIV and Tdap simultaneously or sequentially (IIV followed by Tdap) using a permuted block randomization scheme stratified by Lead and Contributing sites. The project statistician at Duke University will generate permuted block randomization schemes which will be uploaded to REDCap. The randomization schedule will not be available to the study staff, so the next randomization allocation will not be known before randomization occurs. Following confirmation of study eligibility criteria during Visit 1, participant randomization will be through REDCap with treatment allocation recorded on the CRF.

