### **6.3 Influenza Laboratory Analysis**

We intend to utilize the 2016-2017 and 2017-2018 quadrivalent Fluzone (Sanofi) as the IIV study product. As such, reference wild-type, reassortant, or vaccine virus strains representative of the specific viral antigens included in the 2016-2017 and 2017-2018 influenza vaccines will be used to evaluate the relative levels of all four influenza strain-specific antibodies in maternal serum pre- and post-vaccination (60 subjects, 240 samples total). To accomplish these activities all patient samples will be interrogated for influenza antibodies against the strains of interest using the influenza hemagglutination inhibition assay (HI). This assay is considered the “gold-standard” measure by which to evaluate seroconversion/seroprotection in response to seasonal influenza vaccination. This assay will be performed in accordance with the RBL Virology Unit’s fully optimized and approved SOP (RVUSOP004 Influenza HI of Serum Samples). Briefly, test samples will be assayed by HAI as duplicate 2-fold dilution series starting at 1:10. Serum dilutions are then incubated with a concentration of virus verified to possess a known potential for red blood cell (RBC) agglutination. The presence of virus-specific antibodies is visualized via incubation of the virus-serum mixture with a RBC solution; the endpoint titer for a given dilution series is then expressed as the reciprocal of the final dilution in which complete HI is observed. By convention, seronegative samples are defined as having an endpoint HI titer < 1:40 and seropositive samples as having an endpoint titer of ≥ 1:40; and seroconversion as a 4-fold change in endpoint titer relative to pre-immunization baseline or a change from <1:10 to ≥1:40.

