### 7.1 Analysis Plan

**7.1.1 Study Populations** – There will be two study populations for this study. The Intent-to-Treat (ITT) and Safety populations. The ITT Population includes any participant that was enrolled and randomized into the study. The Safety Population is a subset of the ITT Population excluding those participants that never received the study intervention (either the influenza or Tdap vaccine). Statistical analyses will be performed for both study populations, or the ITT Population only if no participants are excluded for the Safety Population.

**7.1.2 Primary Objective 1** - To assess proportions of reactogenicity events in pregnant women receiving Tdap and IIV simultaneously vs. sequentially

Reactogenicity will be assessed for 7 days following each vaccination visit, as described in Section 5.3. The proportion of women and a 95% exact binomial confidence interval will be presented by treatment group, symptom, and grade level (mild/moderate/severe) for women with injection site reactogenicity within 7 days post-vaccination. This will be presented for each of the four reactogenicity outcomes, using the highest grade reported per woman. A 95% confidence interval of the difference in proportions between the treatment groups will also be presented. Systemic reactogenicity will be presented in a similar fashion. For adverse events, the proportion of women and a 95% exact binomial

confidence interval of adverse events, as well as the total number of adverse events, will be presented by treatment group, severity, and relatedness

**7.1.3 Primary Objective 2** - To assess maternal immune responses and cord blood antibody levels to pertussis antigens, tetanus and diphtheria toxoids, and influenza antigens in the women receiving Tdap and IIV simultaneously vs. sequentially

**7.1.3.1 Pertussis antigens** - Geometric mean titers (GMTs) will be calculated along with 95% confidence intervals for the two treatment groups for each pertussis antigen tested. A 95% confidence interval of the difference in GMTs between the treatment groups will also be presented.

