**7.1.3.2 Tetanus and diphtheria antigens** - The proportion of subjects with seroprotection, defined as  $\geq 0.1$  IU/mL post-vaccination for both tetanus and diphtheria ELISAs, in the two treatment groups will be presented along with 95% exact binomial confidence intervals. Ninety-five percent confidence intervals of these differences in proportions between the treatment groups will also be presented. Given there is no acceptable definition of seroconversion with these assays, we will evaluate the data to derive a potential post hoc definition for seroconversion.

**7.1.3.3 Influenza antigens** - The proportion of subjects with seroprotection (pre- and post-immunization) and seroconversion (4-fold change in endpoint titer relative to pre-immunization baseline or a change from  $<1:10$  to  $\geq 1:40$ ) in the two treatment groups will be presented along with 95% exact binomial confidence intervals. A 95% confidence interval of the difference in proportions between the treatment groups will also be presented. The GMTs for each influenza antigen and 95% confidence boundaries will be presented for both treatment groups. A 95% confidence interval of the ratios in GMTs between the treatment groups will also be presented.

Outcomes listed in Primary Objective 2 may be analyzed using a regression model to adjust for covariates such as BMI or race. This will be performed as a secondary analysis if normality assumptions for model based analyses are met.

**7.1.4 Primary Objective 3** – To assess the feasibility of conducting a larger clinical trial in pregnant women receiving Tdap and IIV simultaneously vs. sequentially

Feasibility will be assessed based on the following benchmarks for recruitment and retention in **Table 6**, as well as adequate and timely collection of data and biospecimens.

Table 6: Proposed Feasibility Benchmarks	
Benchmark	Completion Target
Recruitment and randomization	30-50* subjects during 4 month enrollment period
Retention	98% completion of all in-person and delivery visits
Data collection	$\geq 95\%$ collection of reactogenicity data
Biospecimen collection – maternal	$\geq 95\%$ collection of pre/post-vaccination blood samples

Biospecimen collection – delivery	≥ 95% collection of maternal blood, umbilical cord blood, and placental pathology
-----------------------------------	---

\*enrollment target will depend upon whether additional enrollment occurs at the Cincinnati Site

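### The pertussis and influenza GMT comparisons are unadjusted, and neither the Visit 1 titre nor site is prespecified as a covariate; the intervals are valid but may be wider than they need to be

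*Combined protocol and SAP*

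**What the plan says.** Section 7.1.3.1 plans a GMT with 95% CI per arm for each pertussis antigen, then a between-arm interval: "A 95% confidence interval of the difference in GMTs between the treatment groups will also be presented". Section 7.1.3.3 does the same for each influenza strain on the ratio scale: "A 95% confidence interval of the ratios in GMTs between the treatment groups will also be presented". Neither names a covariate.

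Adjustment appears once, at the end of 7.1.3: "Outcomes listed in Primary Objective 2 may be analyzed using a regression model to adjust for covariates such as BMI or race". It has a condition attached: "This will be performed as a secondary analysis if normality assumptions for model based analyses are met". No test, threshold or fallback for that condition is given.

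Two natural covariates are already in the design. Section 5.1 (Visit 1) has blood drawn before vaccination in both arms, and section 5.2.1 allocates "using a permuted block randomization scheme stratified by Lead and Contributing sites". The baseline titre is used in the influenza seroconversion definition but in none of the GMT contrasts.

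The sequential arm also has a second sample before Tdap. At Visit 4 the instruction is "Study participants in sequential group to have blood sample obtained prior to vaccination".

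**The concern.** The Visit 1 titre of the same antigen is usually the first candidate when looking for a covariate that predicts the post-vaccination titre. Site is the factor the randomisation was stratified on. Leaving both out puts whatever variation they explain into the residual and so widens the interval. Section 7 says the pilot was not sized for group comparisons and reports estimates with confidence intervals, so the width of those intervals decides how much the GMT contrasts can say about a possibly reduced pertussis response, which section 1.1 gives as a motivation for the trial.

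Three smaller points follow from the wording:

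- **Open list.** Covariates can be chosen after the data are seen.
- **Normality condition.** Influenza HI titres are endpoints of two-fold dilutions starting at 1:10 (section 6.3), so they are discrete. A strict reading of the condition could cancel the adjusted influenza analysis for a reason that matters little to a linear model at this sample size.
- **Baseline.** For Tdap antigens in the sequential arm, a pre-vaccination sample could mean Visit 1 or Visit 4. The Visit 4 sample is taken after randomisation and after the influenza vaccine, so it should not be the covariate.

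The point covers GMT contrasts only. The seroprotection and seroconversion proportions are outside it, and so are tetanus and diphtheria as currently planned.

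**Working it through.** The plan gives no power, SD or correlation, so there is no stated figure to reproduce. The check compares interval widths.

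**Inputs from the documents**

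- 80 women (Protocol Summary) randomised 1:1 (section 5.2.1), so 40 per arm.
- Section 6.3 gives "60 subjects, 240 samples total" for the influenza assays. Split 1:1, this gives 30 per arm, used as a second case.
- Stratification by two sites; block size not stated.

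**Assumed inputs**

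- ρ, the correlation of Visit 1 with post-vaccination log titre: 0, 0.3, 0.5, 0.7.
- SD of the natural-log titre: 1.0, with 0.8 and 1.2 as sensitivity values.

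**Formulas** (half-width of the 95% CI for the log GMT ratio, n per arm)

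- Unadjusted: t(0.975, 2n−2) × SD × √(2/n)
- Adjusted for Visit 1 titre and site: t(0.975, 2n−4) × SD × √(1−ρ²) × √(2/n) × √(1 + 1/(2n−4))

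The last factor is the expected cost of chance imbalance in the covariate. Site is taken to have no effect on titre.

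**Worked case: n = 40, SD = 1.0, ρ = 0.5**

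- Unadjusted: 1.9908 × 1.0 × 0.2236 = 0.445; exp(0.445) = 1.56
- Adjusted: 1.9917 × 1.0 × 0.8660 × 0.2236 × 1.0066 = 0.388; exp(0.388) = 1.47
- Width ratio: 0.388 / 0.445 = 0.872, which is 12.8% narrower

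**All cases, SD = 1.0** (CI factor: the GMT ratio multiplied and divided by this number)

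| ρ | 40 per arm: width ratio | 40 per arm: CI factor | 30 per arm: width ratio | 30 per arm: CI factor |
|---|---|---|---|---|
| unadjusted | 1 | 1.56 | 1 | 1.68 |
| 0 | 1.007 | 1.57 | 1.010 | 1.69 |
| 0.3 | 0.961 | 1.53 | 0.963 | 1.65 |
| 0.5 | 0.872 | 1.47 | 0.874 | 1.57 |
| 0.7 | 0.719 | 1.38 | 0.721 | 1.45 |

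The SD cancels from the width ratios. It does change the CI factors: at ρ = 0.5 and 40 per arm, SD 0.8 gives 1.43 falling to 1.36, and SD 1.2 gives 1.71 falling to 1.59.

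**Sample-size equivalent.** By variance alone, 80 women analysed with adjustment match 80/(1−ρ²) analysed without it: 80/0.91 ≈ 88, 80/0.75 ≈ 107 and 80/0.51 ≈ 157 for ρ = 0.3, 0.5 and 0.7.

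**Simulation.** 5,000 trials per scenario; 80 women; assumed site split 50/30, blocks of 4 and log10 SD 0.5.

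| | No site effect | Site effect 0.3 log10 (assumed) |
|---|---|---|
| Coverage, unadjusted | 94.6–95.2% | 95.8–96.3% |
| Width ratio at ρ = 0, 0.3, 0.5, 0.7 | 1.01, 0.96, 0.87, 0.72 | 0.97, 0.92, 0.84, 0.69 |

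Coverage of the adjusted interval was 94.4–95.4% across all scenarios. Both analyses are therefore valid. The unadjusted interval is slightly conservative when sites differ, because the stratified allocation is ignored.

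**The case against.** The strongest reply is that nothing here is an error. The pilot disclaims power for group comparisons, no stated decision depends on the width of a GMT interval, and the feasibility targets in Tables 6 and 7 concern recruitment, retention, collection and testing. The open covariate list already permits Visit 1 titre and site. The benefit is assumed throughout: at ρ = 0.3 the CI factor moves only from 1.56 to 1.53, and the gain may be smaller at delivery and in cord blood if the correlation with Visit 1 is lower there. All of that is true. It limits the weight of the point but does not remove it, because the intervals are the planned output for these contrasts and permitting a covariate is not the same as fixing it in advance.

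Four technical replies deserve an answer:

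- **Scale.** The pertussis text plans a difference in GMTs, while every width above is for a log-scale ratio. This is fair. The figures and the coverage check apply to a ratio only, and the mismatch of scale between the two sections is a separate matter.
- **Baseline.** The Visit 1 versus Visit 4 ambiguity does not touch the planned unadjusted pertussis contrast, which uses no baseline. It bites only once a baseline is used, and then one sentence settles it.
- **Assay floor.** Low baseline HI titres pile up at the starting dilution, which can weaken the covariate. That lowers the effective ρ and the gain.
- **Season.** Charging season the full chance-imbalance cost gives about 1.4% (40 per arm) or 1.9% (30 per arm) extra width at ρ = 0. A simulation with permuted blocks of 4 by site and season in the model gave width ratios from 1.008 (ρ = 0) to 0.718 (ρ = 0.7) at 40 per arm, and from 1.010 to 0.724 at 30 per arm. Blocking removes most of that cost.

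**Conclusion.** The concern holds, as a point about efficiency and prespecification. The planned unadjusted GMT contrasts are unbiased, and their log-scale intervals have correct coverage. Adjustment for Visit 1 titre and site costs about 1% in width if neither predicts the outcome. It narrows the log-scale interval by about 4%, 13% or 28% if ρ is 0.3, 0.5 or 0.7, and somewhat more if sites differ in titre. These sizes rest on assumed values of ρ and, for the CI factors, of the SD; the documents give neither. No gain is claimed for the proportions. The change should be made because the data are already being collected and the downside is small, but no conclusion of the pilot is invalid without it.

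**What to change.** In section 7.1.3, for each antigen and time point analysed as a titre:

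1. Prespecify an ANCOVA of log titre on arm, Visit 1 log titre of the same antigen and site, with season added for the influenza antigens.
2. Report the result as an adjusted GMT ratio with 95% CI, beside the planned unadjusted contrast.
3. State that the Visit 1 sample is the baseline in both arms for every antigen, and that the sequential arm's Visit 4 sample is not used as a covariate.
4. Remove the normality condition for this model and use robust standard errors if needed.
5. Leave the seroprotection and seroconversion proportions as planned.

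The cost is SAP wording only: no new visits, samples, participants or data. The statistical price in the worst case is an adjusted interval about 1% wider, with the unadjusted one still reported next to it.

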**7.2 Data Management**

The amount of data that will be collected for the proposed project will be substantial and will require a sophisticated, practical and flexible system that can accommodate different modes of data collection and several separate linked surveys. The novel Vanderbilt-designed resource developed specifically for online collection of research information,

the Research Electronic Data Capture (REDCap) platform, will be used to design study forms, including the reaction forms, and short customized questionnaires to collect information from study subjects. This system will be used by Duke for data management. All electronic linkages will fulfill regulations for protection of human subjects and requirements to minimize the risk of breach of confidentiality. After initial set-up, the work load required for electronic data collection will be substantially reduced (description of REDCap resources below). Duke investigators have previously used the REDCap system for collection and analysis of large quantities of data. Participants will be given the option to fill out their reactogenicity diary either directly in the REDCap system or on paper. Participants who choose the paper form will receive phone calls (Visits 2, 3, 5, and 6) to collect the information recorded on their diary card, which will then be entered by study personnel onto REDCap. Participants who choose to enter the information directly into REDCap will receive phone calls if they fail to enter their information. All study-related documents containing protected health information, e.g. enrollment logs, case report forms, memory aids (Appendix B-E) completed by study participants, will be maintained in secure research offices at Duke, which are accessible to research staff only.

The study team will utilize a secure, encrypted, file transfer method for sharing study documents and data with the CDC Pertussis laboratory and study teams. No personal identifiers will be included in any shared documents or datasets.

### **7.2.1 Research Electronic Data Capture (REDCap)**

Investigators within the NIH-funded Clinical and Translational Research Unit at Vanderbilt have developed REDCap (<http://project-redcap.org/>), to collect and manage data for diverse clinical and translational research studies. REDCap was designed around the concept of giving research teams an easy method to specify project needs and rapidly develop secure, web-based applications for collection, management and sharing of research data. REDCap accomplishes these key functions through use of a single study metadata table referenced by presentation-level operational modules. Based on this abstracted programming model, databases are developed in an efficient manner with little resource investment beyond the creation of a single data dictionary. The concept of metadata-driven application development is well established, and the critical factor for successful data collection lies in creating a simple workflow methodology allowing research teams to autonomously develop study-related metadata in an efficient manner. Of particular interest for this project, a subcomponent of REDCap, the REDCap Survey is designed for studies where data are collected directly from the research participant. This will be used with the web-based reaction forms that will be completed by the study subjects. Both products include secure institutional data hosting and include full audit-trails in compliance with HIPAA security requirements. The REDCap Consortium is comprised of 647 active institutional, including CCHMC. The REDCap currently supports 68,000 projects with over 89,000 users spanning numerous research focus areas across the consortium. The current project will use this software application for the design of electronic forms to collect information from study participants, to link the baseline data, sample collection date, and laboratory results in an automated database family, to perform data cleaning and data quality assurance efficiently, and to design an analytical dataset for the analysis of the project data.

Data will be entered into the REDCap database by members of the study team, from Duke and Cincinnati using the paper case report forms utilized to record data collected

as part of study procedures. Study investigators will be responsible for assuring that all paper records are securely stored according to the requirements of their IRBs. The study investigators will be responsible for assuring the accuracy of the data entered from the paper forms into REDCap. Only the assigned identifiers will be used in REDCap. Therefore, personal health identifiers will not appear in the REDCap database.

In order to perform data cleaning and data quality assurance efficiently, numerous built-in filters and checks for consistency of the data including range and limit checks, branching logic and pull down menus to limit choices for categorical variables to a pre-specified list will be implemented and performed automatically to minimize data entry error. The data will be randomly sampled and checked against source records on a regular basis. The data and related analytical datasets will also be stored at the lead and contributing sites with secured password-protected computers. Coded data without personal identifiers will be made available to the CDC and transferred using a secure transfer method as described in Section 7.2.

